1.5. Collected On Therapists and Research Staff Providing DSW and In-Person MFG

1.5.1. Therapist/staff Contact Time. All therapists will keep a log of all contacts they have with participants in both arms of the study. This will include the date, amount of time and purpose of the contact. For the in-person MFG treatment this will also include time in the sessions. Research staff will also keep track of all contact with participants in all arms and the reasons for the contact.

1.5.2. Therapists & Research Staff Time Providing the Treatments. All therapists will keep detailed records of all activities and the time involved with each activity to provide each of the two treatments, including preparation time, any calling of participants and meetings, time on DSW, etc. This will allow analyses of the clinician time requirements for each treatment. In addition, we will track research staff time involved with each treatment to identify the types and amount of potential “overhead” effort involved in providing each treatment.

1.6. Data Management

The PI will oversee all aspects of data management. The MIRECC Data Center (DC), PI, data manager, and study coordinator will develop a Manual of Operations (MOP) to standardize all staff training and procedures. Study forms will be paper. Completed forms will be stored in a locked file cabinet where only select research team members will have access.

1.8. Power, Sample Size, with Estimation of Missing Subjects Follow-up

The primary Veteran outcomes are SAPS and SANS, and family outcome is caregiver burden. Note, for these outcome measures higher scores indicate worse symptoms. The equivalence ratio that will be tested is the mean of DSW/mean of in-person MFG. For both Veterans and family members we plan for the study to detect equivalence ratios of 1.2 for the two measures of psychotic symptoms (SAPS and SANS) and caregiver burden. In these hypotheses tests the null hypotheses are that DSW outcome means are inferior to MFG. The ‘alternative’ hypotheses are that outcomes means in the DSW arm are equivalent to outcomes in the in-person MFG arm. If as an example, the symptoms are higher in the DSW arm, and thus the ratio of the mean of the DSW arm to the mean of the in-person MFG arm exceeds 1.2 (i.e. mean of DSW > mean in-person MFG by 20% or more) we will accept the null hypothesis that the mean of DSW > mean of in-person MFG, and that DSW is not as effective as in-person MFG. Any ratio of DSW/MFG that is < 1.2 will cause us to reject the null hypothesis and accept the alternative that they are equivalent. For the caregiver burden scale the equivalence ratio that leads to rejection is slightly smaller, it is 1.17 because there is only 1 primary measure. With 42 subjects per treatment arm, power is >80% with one tailed alpha =0.025 to detect equivalence ratios of 1.2 (and above). For testing whether DSW is superior to in-person MFG on the illness symptom measures we can reverse the ratio and test whether (mean of in-person MFG/mean DSW) is > 1.20. For these sample size calculation we used reported data to estimate the coefficients of variation (CV) of the scales. CVs commonly range from 0.3-0.5 and within this range there were differences in the calculated equivalence ratios. For alpha =0.025, and CV equal to 0.3 the equivalence ratio bound was 1.20 with an increase to 1.29 for a CV of 0.5.

For the in-person MFG arm a correction for nesting of subjects in a group is needed, which increases the number of subjects required. If it is assumed that this dependency is 0.01 and groups are of size 6-8 then variance inflation factor is on the order of 10%, resulting in 46-47 subjects being needed for the in-person MFG arm. Because DSW is available separately for each Veteran and family member it is not necessary to increase the 42 subjects needed for this group. The

42 and 47 subjects per treatment arm respectively (n=89 total) represent the number of Veterans that need to complete their assigned interventions. We expect that the non-completion rate for the in-person MFG arm to be $\leq 33\%$ and DSW arm to be $\leq 10\%$. Given these estimates 70 in person MFG subjects will be enrolled and 47 DSW subjects, for a total of 117 to account for attrition and non-completers. Sample size calculations used PASS (2008, NCSS, LLC, Kaysville Utah.).

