1.7. Data Analysis

Overview. Initially we will assess whether our stratified randomization procedures yielded groups equivalent in groups on the stratification factors and other demographic and clinical variables. These analyses will be completed with chi-square statistics for categorical variables (or Fisher Exact statistics as needed for small ns) and t-tests for continuous measures (or Kruskal-Wallace tests if there are serious deviations from normality on these variables). Our initial analyses of the primary dependent measures for Veterans, the SAPS and SANS, and for family members/supporters, Caregiver Burden, will test the mean ratios at time points 12 and 15 months to test for non-inferiority. Then the analyses will be move to mixed effect regressions with the primary effects of interest the interaction between time of measurement and treatment group. The use of mixed effect regression allows us to include subjects with partially complete data, e.g. missing the 6 month interview but have baseline, and 12 month interview data available (see below). Prior to the regression analyses we will also check to insure that the continuous measures (SAPS, SANS, Caregiver Burden) are normally distributed. If these assumptions are violated we will identify appropriate transformations to normalize these outcomes or use different forms of the outcome variables and regression techniques that do not require normality to be appropriate. Also of interest will be differences between completers vs. non-completers across the 2 groups as well as within groups (see specifics below under Aims 1 and 2).

1.7.1. Specific Aim 1

We will conduct a 2-arm, non-inferiority randomized comparative effectiveness trial of DSW and in-person multi-family MFG. We will compare changes in severity of Veterans' of psychiatric symptoms (i.e., positive and negative symptoms), and caregiver psychological burden, during the treatment period and then 3-months post-treatment.

Hypothesis 1.1. Veterans participating in DSW will do as well or better than those participating in in person MFG with an equivalence ratio of 1.20-1.47 (depending on the coefficients of variance of the measures assessed) at time points 12 and 15 months.

Hypothesis 1.2. Family caregivers participating in DSW will do as well as or better than those participating in in-person MFG with an equivalence ratio of 1.17-1.29 (depending the coefficient of variance of the measure assessed) at time points 12 and 15 months.

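### The non-inferiority rule compares the DSW/MFG ratio itself with 1.2; as written it passes a DSW exactly at the margin about 50% of the time, against a stated alpha of 0.025

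*Combined protocol and SAP*

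**What the plan says.** Section 1.8 defines the tested quantity as the DSW mean divided by the in-person MFG mean, with higher scores worse and inferiority of DSW as the null hypothesis. It then gives a two-way rule. If the ratio "exceeds 1.2 (i.e. mean of DSW > mean in-person MFG by 20% or more) we will accept the null hypothesis". In the other direction, "Any ratio of DSW/MFG that is < 1.2 will cause us to reject the null hypothesis and accept the alternative that they are equivalent".

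The same paragraph gives the design's error rates: "With 42 subjects per treatment arm, power is >80% with one tailed alpha =0.025 to detect equivalence ratios of 1.2 (and above").

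For caregiver burden, the section first says the study should "detect equivalence ratios of 1.2 for the two measures of psychotic symptoms (SAPS and SANS) and caregiver burden". It later says that for this scale "the equivalence ratio that leads to rejection is slightly smaller, it is 1.17 because there is only 1 primary measure".

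Section 1.7 says only that the first analyses "will test the mean ratios at time points 12 and 15 months to test for non-inferiority". In section 1.7.1, Hypothesis 1.1 is framed "with an equivalence ratio of 1.20-1.47 (depending on the coefficients of variance of the measures assessed"), and Hypothesis 1.2 "with an equivalence ratio of 1.17-1.29 (depending the coefficient of variance of the measure assessed").

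**The concern.** A non-inferiority test at level alpha must allow for sampling error. The estimate has to fall far enough below the margin that a true ratio at the margin would be passed with probability of at most alpha. The written rule has no such allowance. It also has no inconclusive outcome: every ratio other than exactly 1.2 leads either to a claim of equivalence or to acceptance of inferiority.

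At stake is the main claim of the trial, that the website does as well as in-person treatment. One analyst following the sentence and another following the stated alpha could reach opposite conclusions from the same data. The unsettled margin adds to this. If the margin follows the CV, noisier data earn a looser standard, and the cut-off could be chosen after the data are seen.

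**Working it through.** **Inputs from section 1.8:** margin 1.2 (caregiver burden 1.17), one-sided alpha 0.025, power above 80%, 42 per arm, CV 0.3 to 0.5. **Assumptions:** log-normal outcome, unadjusted and unclustered comparison, one measure at one time point. The power figures also assume a true ratio of 1.0, which the documents do not state.

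**Standard error of the log ratio:** SE = √ln(1+CV²) × √(2/42).
- CV 0.3: 0.2936 × 0.2182 = 0.0641
- CV 0.4: 0.3853 × 0.2182 = 0.0841
- CV 0.5: 0.4724 × 0.2182 = 0.1031

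**1. The plan's own figure.** With margin 1.2, CV 0.3 and one-sided 0.025, the noncentrality is ln(1.2)/0.0641 = 2.846. The noncentral t on 82 df gives 80.3% power at 42 per arm (79.3% at 41). The stated sample size therefore reproduces, and it belongs to a formal 0.025 test.

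**2. The written rule.** P(pass | true ratio R) = Φ[(ln 1.2 − ln R)/SE].

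| True ratio | CV 0.3 | CV 0.5 |
|---|---|---|
| 1.20 | 50% | 50% |
| 1.25 | 26% | 35% |

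At R = 1.0 and CV 0.3 it passes 99.8%. At R = 1.2 the numerator is zero, so the 50% holds for any CV or sample size. Against 2.5% it is 20 times too high. Simulations of 200,000 trials per setting, using the ratio of arithmetic means, gave 49.9% to 50.2% at R = 1.2 for log-normal and normal data, with arms of 42/42 and 42/47. The result does not depend on the log-normal model.

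**3. What a 0.025 test would require.** Largest passing observed ratio = 1.2 × exp(−1.989 × SE).
- CV 0.3: 1.056
- CV 0.4: 1.015
- CV 0.5: 0.978

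**4. One result read two ways.** For an observed ratio of 1.10, the upper 97.5% limit is 1.10 × exp(1.989 × SE) = 1.25, 1.30 and 1.35 at CV 0.3, 0.4 and 0.5. All exceed 1.2, so the formal test fails each time while the written rule declares equivalence.

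**5. The confidence-limit rule.** Requiring the upper one-sided 97.5% limit to be below 1.2 gave a simulated pass rate of 2.5% at R = 1.2. Power at R = 1.0 is 80% at CV 0.3, 57% at CV 0.4 and 42% at CV 0.5.

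**6. Caregiver burden at 1.17.** The written rule again passes 50% at a true ratio of 1.17. A formal test at CV 0.3 with 42 per arm has 68% power at one-sided 0.025 and 78% at 0.05. Reaching 80% takes 56 or 44 per arm respectively.

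**The case against.** The best defence is that the sentence divides the parameter space and was never meant as a rule for the estimate. It does not say observed or estimated, it sits in the power section, and it follows a statement of the null hypothesis. The stated alpha and the reproducible 42 per arm both point to a formal test. That makes a formal test the probable intent. It does not supply the criterion: a ratio that causes rejection reads most naturally as the observed one, and no other text says which limit is compared with which margin.

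On caregiver burden, the remark about a single primary measure suggests that this outcome was planned at 0.05, with 0.025 being 0.05 split over SAPS and SANS. The figures support this. At 0.05 and 42 per arm, the margin giving 80% power is 1.174 at CV 0.3 and about 1.29 at CV 0.5, close to the range in Hypothesis 1.2. On that reading the 78% is largely rounding of 1.174 to 1.17, and the 68% applies only if 0.025 was meant. The documents never state a separate alpha, so it needs to be named.

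The ranges in Hypotheses 1.1 and 1.2 may be detectable margins carried over from the power calculation. They are nevertheless written into the hypotheses and need reconciling.

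The critical ratios assume 42/42 without clustering. With the planned 42/47 completers, still without clustering, they become 1.060, 1.020 and 0.983, and 1.10 still fails. The 50% is per measure and time point. The documents do not say how SAPS and SANS, or 12 and 15 months, combine, so the trial-level error rate cannot be given.

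**Conclusion.** The concern holds: the rule is wrong as written and must be fixed. For each measure and time point it has an error rate of about 50% at the margin, against the stated 2.5%, and that figure needs no assumption about CV, arm size or distribution shape beyond an approximately symmetric estimate. It is also not the test the trial was sized for (99.8% against 80.3% passing at a true ratio of 1.0 and CV 0.3). Those two figures rest on the assumed true ratio and the log-normal model. Separately, no outcome has one cut-off stated consistently: SAPS and SANS have 1.2 or 1.20–1.47, and caregiver burden has 1.2, 1.17 or 1.17–1.29. The finding concerns the written criterion and does not claim that the authors intended to judge the trial on the point estimate.

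**What to change.** Replace the sentence in section 1.8 with:

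> For SAPS and SANS, non-inferiority is concluded only if the upper one-sided 97.5% confidence limit of the DSW/MFG ratio of means is below 1.2; otherwise non-inferiority is not shown.

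Add the same form for caregiver burden with margin 1.17 and its own named alpha: either the stated 0.025 (97.5% limit), or 0.05 (95% limit) if the team assigns that to this outcome. Restate its power to match (68% or 78% at CV 0.3 with 42 per arm). Fix one margin per outcome in advance, removing the ranges from Hypotheses 1.1 and 1.2 and the second caregiver figure of 1.2. In the same edit, say at which time point the rule applies and how the two symptom scales and the two time points combine.

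The cost is wording and a restated power section, with no new data. The claim becomes harder to win than under the literal rule. With margin 1.2 held at 0.025 and a true ratio of 1.0, power falls to 57% at CV 0.4 and 42% at CV 0.5, and the power section should say so. If 80% power is wanted for caregiver burden at 1.17 and CV 0.3, it takes 56 per arm at 0.025 or 44 per arm at 0.05.

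### The caregiver-burden bounds of 1.17 to 1.29 fit a one-sided alpha of 0.05, but the only alpha stated for the non-inferiority tests is 0.025, and burden has two thresholds (1.2 and 1.17)

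*Combined protocol and SAP*

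**What the plan says.** All of this is in Section 1.8 unless noted.

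- **Scale of the test.** "The equivalence ratio that will be tested is the mean of DSW/mean of in-person MFG", with higher scores worse.
- **Common target.** "we plan for the study to detect equivalence ratios of 1.2 for the two measures of psychotic symptoms (SAPS and SANS) and caregiver burden".
- **Separate threshold for burden.** A few sentences later, for the caregiver scale, "the equivalence ratio that leads to rejection is slightly smaller, it is 1.17 because there is only 1 primary measure". No alpha or power accompanies this figure.
- **Power statement.** "With 42 subjects per treatment arm, power is >80% with one tailed alpha =0.025 to detect equivalence ratios of 1.2 (and above".
- **CVs.** "CVs commonly range from 0.3-0.5 and within this range there were differences in the calculated equivalence ratios". No CV specific to the burden scale is given.
- **Bounds tied to an alpha.** "For alpha =0.025, and CV equal to 0.3 the equivalence ratio bound was 1.20 with an increase to 1.29 for a CV of 0.5".
- **Section 1.7.1, Hypothesis 1.2.** Caregivers in the website arm (DSW) are to do at least as well as those in the in-person group arm (MFG) "with an equivalence ratio of 1.17-1.29 (depending the coefficient of variance of the measure assessed" at 12 and 15 months.

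The document states one other alpha, 0.05, in Section 1.7.2. It belongs to the exploratory Aim 2 regressions.

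**The concern.** The reason given for the smaller burden ratio is incomplete. For a given sample size, CV and power, the detectable ratio depends on alpha. Having one primary measure rather than two matters only if it changes alpha, so the sentence implies a larger alpha for burden that is written nowhere. In addition, 1.29 appears twice in different roles: as the upper burden bound in Hypothesis 1.2, and in Section 1.8 as the CV 0.5 bound at alpha 0.025. If the burden range was computed at another alpha, the second use is wrong.

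Caregiver burden is the primary family outcome. From the present text an analyst cannot tell whether to use a two-sided 95% interval (one-sided 0.025) or a 90% interval (one-sided 0.05), or whether to compare its upper limit with 1.2, 1.17 or a value that depends on the observed CV. Those choices can reverse the non-inferiority conclusion on the same data.

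**Working it through.** **Inputs from Section 1.8:** 42 per arm; CV 0.3 and 0.5; one-sided alpha 0.025; power 80%. One-sided 0.05 is tried as the alternative. **Assumed, because the plan does not state it:** true ratio 1, log-normal data, and 42 caregivers per arm (the plan's counts are of Veterans).

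**Formulas.** On the log scale

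- σ = √ln(1 + CV²), so σ = √ln 1.09 = 0.2936 at CV 0.3 and √ln 1.25 = 0.4724 at CV 0.5
- SE = σ·√(2/42) = σ × 0.2182, so SE = 0.0641 and 0.1031
- 80%-power bound ≈ exp[(z(1−α) + 0.8416)·SE]
- power for ratio R ≈ Φ[ln R / SE − z(1−α)]

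The t results below replace the normal by the noncentral t with 82 degrees of freedom and noncentrality ln R / SE.

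**Step 1: reproduce the plan's own figure.** At alpha 0.025 and CV 0.3 the bound is exp(2.8016 × 0.0641) = 1.197 (normal) or 1.199 (t). Power for 1.20 is 81.2% (normal) or 80.3% (t), and 42 per arm is the number the t calculation requires. The plan's 1.20 is recovered, so the model fits its calculation.

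**Step 2: bounds under each alpha.**

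| One-sided alpha | CV 0.3: normal / t | CV 0.5: normal / t |
|---|---|---|
| 0.025 | 1.197 / 1.199 | 1.335 / 1.339 |
| 0.05 | 1.173 / 1.174 | 1.292 / 1.295 |
| Plan, burden | 1.17 | 1.29 |

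Both ends of the burden range match the 0.05 row. Neither matches the 0.025 row.

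**Step 3: power for the burden ratios.**

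- R = 1.17, CV 0.3, alpha 0.025: ln 1.17 / 0.0641 = 2.451, and Φ(2.451 − 1.960) = 68.8% (t: 67.8%).
- R = 1.29, CV 0.5, alpha 0.025: ln 1.29 / 0.1031 = 2.470, and Φ(2.470 − 1.960) = 69.5% (t: 68.5%).
- At alpha 0.05 the same two cases give 79.0% and 79.5% (t: 78.4% and 79.0%).

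Reaching 80% at 0.025 would take about 56 and 55 per arm respectively.

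**Step 4: the sentence that names alpha 0.025.** It gives 1.20 at CV 0.3, which is the 0.025 result, and 1.29 at CV 0.5, which is the 0.05 result. At 0.025 the second figure should be about 1.34.

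**Step 5: other models at alpha 0.025 (CV 0.3 / CV 0.5 bounds).** Allocation 42:47 on the log scale, 1.193 / 1.329; difference scale, 1.186 / 1.309; Fieller-type ratio on the raw scale, 1.206 / 1.371; two-sided equivalence, 1.233 / 1.401. None gives 1.17 / 1.29. Power for 1.17 at CV 0.3 ranges from 65.5% to 72.8% over the non-inferiority variants.

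**Step 6: a single fixed margin for burden (t, 42 per arm).**

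| Margin | Alpha 0.025: CV 0.3 / CV 0.5 | Alpha 0.05: CV 0.3 / CV 0.5 |
|---|---|---|
| 1.20 | 80% / 42% | 88% / 54% |
| 1.17 | 68% / 32% | 78% / 45% |

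**The case against.** The strongest reply is that the plan's reason is shorthand for a multiplicity rule: 0.05 is shared between SAPS and SANS, 0.025 each, while the single burden measure keeps 0.05. On that reading 1.17 and 1.29 are right to rounding and the burden figures contain no arithmetic error. This is plausible, and the numbers support it. But it has to be inferred, because no sentence assigns 0.05 to burden. It also leaves two faults standing: 1.29 at CV 0.5 is expressly attributed to alpha 0.025, and burden carries both 1.2 and 1.17.

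A second reply is that the match to 0.05 depends on CVs of exactly 0.3 and 0.5. That is correct. At 0.025, CVs of about 0.26 and 0.43 would also give 1.17 and 1.29. The first lies below the plan's stated range, however, and Section 1.8 pairs 1.29 with CV 0.5.

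Two stronger readings are tempting, and the documents support neither:

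- **That the plan claims more than 80% power for 1.17 and is wrong.** Its power statement covers ratios of 1.2 and above, and 1.20 at CV 0.3 reproduces. For 1.17 no power is stated.
- **That burden is to be tested at double the only alpha in the plan.** Section 1.7.2 also states 0.05, though for exploratory regressions, and the level for burden is undeclared rather than set at 0.05.

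**Conclusion.** The point stands as an inconsistency between alpha, margin and detectable ratio for caregiver burden.

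- The range 1.17 to 1.29 corresponds to one-sided 0.05 at the plan's CVs and 42 per arm, whereas 0.025 is the only level stated for any non-inferiority test.
- The 1.29 that Section 1.8 ties to alpha 0.025 should be about 1.34. This needs no inference about which alpha was meant for burden.
- The text gives burden two thresholds, 1.2 and 1.17.

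If 0.025 applies to burden, power is about 10 percentage points lower than at 0.05: about 68% to 69% for 1.17 at CV 0.3, and about 69% for 1.29 at CV 0.5.

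These figures assume a true ratio of 1 and log-normal scores; the recovery of 1.20 with 42 per arm supports both. They also assume one caregiver per Veteran. Fewer caregivers would widen the bounds. Confidence is high on the bounds and lower on which alpha the sponsor intended.

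**What to change.** State one alpha and one margin for caregiver burden, in Section 1.8 and in Hypothesis 1.2.

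- **If one-sided 0.025:** restate the detectable ratios as about 1.20 (CV 0.3) to 1.34 (CV 0.5), or keep 1.17 and state its power as about 68% to 69% at CV 0.3. Use a two-sided 95% interval.
- **If one-sided 0.05 is intended, because burden is a single measure while SAPS and SANS share 0.05:** say so, and complete the present explanation rather than delete it. Keep 1.17 to 1.29, labelled as bounds at 0.05 with power of about 78% to 79%, and use a two-sided 90% interval for burden.

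In either case, change the 1.29 given for CV 0.5 at alpha 0.025 to about 1.34, and reconcile the 1.2 target with the 1.17 threshold. It would help to give the power of the chosen margin at both ends of the CV range.

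The cost is wording and, under 0.025, a somewhat less favourable stated figure. No more patients are needed.

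### At the fixed 1.2 rule for SAPS and SANS, the stated >80% power holds only at a CV of about 0.30; at CVs of 0.4 and 0.5, within the plan's own range, it is about 57% and 42%

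*Combined protocol and SAP*

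**What the plan says.** Section 1.8 sets the SAPS and SANS rule without reference to variability: "Any ratio of DSW/MFG that is < 1.2 will cause us to reject the null hypothesis and accept the alternative that they are equivalent". A ratio above 1.2 leads to the conclusion that DSW is not as effective as in-person MFG. For caregiver burden the bound is smaller: "it is 1.17 because there is only 1 primary measure".

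The power statement names a sample size, an alpha and a ratio, but no CV: "With 42 subjects per treatment arm, power is >80% with one tailed alpha =0.025 to detect equivalence ratios of 1.2 (and above").

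Later in the same paragraph the plan turns to variability: "CVs commonly range from 0.3-0.5 and within this range there were differences in the calculated equivalence ratios". It then gives two bounds: "For alpha =0.025, and CV equal to 0.3 the equivalence ratio bound was 1.20 with an increase to 1.29 for a CV of 0.5".

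Section 1.7.1 words the margin differently. Hypothesis 1.1 (Veterans) uses a ratio of 1.20 to 1.47 and Hypothesis 1.2 (caregivers) a ratio of 1.17 to 1.29, each said to depend on the CV of the measure.

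**The concern.** Two quantities are being mixed. One is the power of the rule that decides the trial, a ratio of 1.2. The other is the bound that 42 per arm can detect at a set power, which grows with the CV. Section 1.8 fixes the first and then reports how the second moves. For CVs above 0.3 a reader gets a wider bound, but not the chance that the trial passes at 1.2.

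SAPS and SANS are the primary Veteran outcomes, and Section 1.8 reads a failure at 1.2 as DSW being less effective. If power at 1.2 is well below 80%, a DSW that is truly the same as MFG could often fail, and a reader who relied on the stated >80% would take that failure as evidence against DSW.

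**Working it through.** **Inputs from Section 1.8.** 42 per arm; one-sided alpha 0.025; margin 1.2 (SAPS, SANS) or 1.17 (burden); CV 0.3 to 0.5.

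**Assumptions not in the documents.** True ratio 1.0 (the plan says only that the arms are equivalent under the alternative); analysis on the log scale.

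**Formulas.** Log-scale SD: s = sqrt(ln(1 + CV²)). Standard error: s × sqrt(2/42) = s × 0.2182. Noncentrality: ln(1.2)/SE = 0.1823/SE. Power is the probability that a noncentral t with 82 df exceeds the critical value 1.989.

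**Step 1: the plan's own figure.** At CV 0.3, s = sqrt(ln 1.09) = 0.2936, SE = 0.0641, noncentrality = 2.846 and power = 80.3%. With 41 per arm it is 79.3%, so 42 is the smallest size that reaches 80%. The plan's sample size is therefore the CV 0.3 calculation. Power falls below 80% once the CV passes about 0.301.

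**Step 2: the same rule over the plan's CV range.**

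| CV | s | SE | Noncentrality | Power at 1.2 |
|---|---|---|---|---|
| 0.30 | 0.2936 | 0.0641 | 2.846 | 80.3% |
| 0.35 | 0.3399 | 0.0742 | 2.458 | 68.0% |
| 0.40 | 0.3853 | 0.0841 | 2.169 | 57.3% |
| 0.45 | 0.4294 | 0.0937 | 1.946 | 48.5% |
| 0.50 | 0.4724 | 0.1031 | 1.769 | 41.6% |

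Power crosses 50% at a CV of about 0.44. Holding 80% at 1.2 would take 72 per arm at CV 0.4 and 107 at CV 0.5.

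**Step 3: sensitivity to method.** Power at CV 0.3 / 0.4 / 0.5:

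- Normal approximation: 81.2 / 58.3 / 42.4%.
- 42 DSW and 47 MFG completers, MFG variance inflated by the plan's approximate 10%: 80.7 / 57.7 / 41.9%. With inflation of 6% (a dependency of 0.01 and groups of 7: 1 + 6 × 0.01 = 1.06): 81.4 / 58.5 / 42.6%.
- Original-scale difference of 20% of the mean, SD = CV × mean: 85.5 / 62.0 / 44.1%.
- Ratio test on the original scale (normal approximation): 79.0 / 54.6 / 38.2%.

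No variant at alpha 0.025 reaches 80% at CV 0.35 or above; the most favourable, the original-scale difference, gives 73.5% there.

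**Step 4: the wider bound at CV 0.5.** At a margin of 1.29, noncentrality = ln(1.29)/0.1031 = 2.470 and power is 68% at alpha 0.025. The bound that gives 80% there is about 1.34. One-sided alpha 0.05 does return 1.29.

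**Step 5: the burden bound.** With ln(1.17) = 0.1570 and alpha 0.025, power is 67.8%, 45.5% and 32.5% at CV 0.3, 0.4 and 0.5. At one-sided alpha 0.05 it is 78.4% at CV 0.3, where the 80% bound is 1.174. So 1.17 matches roughly 80% power only at alpha 0.05 and CV 0.3.

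**The case against.** The strongest reply is that the plan discloses the dependence on CV. The paragraph itself attaches 1.20 to CV 0.3 and says that the bound rises with CV. The words in parentheses at the end of the power sentence can be read as allowing larger ratios at higher CVs, and Hypotheses 1.1 and 1.2 state CV-dependent ratios outright. On that reading 80% power is kept by widening the margin, and the 57% and 42% figures describe a test that the plan does not intend. The stated figure also reproduces, so the sum behind it is not wrong.

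Much of this stands. A reader might infer that the plan claims >80% power whatever the CV, or that it conceals the dependence; the paragraph taken as a whole supports neither. A reader might also infer that the trial is underpowered. That cannot be shown, because the documents give no CV for SAPS, SANS or burden individually. Nor is an identical DSW more likely to fail than pass across the upper half of the CV range: on the log scale that is so only above about 0.44, and at 0.40 power is still 57%.

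The disclosure does not settle the matter, however. It reports a detectable bound, while Section 1.8 decides success at 1.2 at any CV. If the margin does widen, the fixed rule in Section 1.8 is not the rule, and the standard becomes easier to meet as measurements become noisier. Even then, the 1.29 given for CV 0.5 delivers only about 68% power at the stated alpha.

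Reading the rule as a comparison of the point estimate with 1.2 does not help either: when the true ratio is 1.2 it would pass about half the time, which is incompatible with alpha 0.025.

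**Conclusion.** The concern holds, conditional on the fixed 1.2 rule in Section 1.8. Under that rule the stated power is correct at a CV of about 0.30 and too high over the rest of the plan's range: short of 80% by about 12 percentage points at 0.35, 23 at 0.40, 32 at 0.45 and 38 at 0.50. The nesting correction leaves this essentially unchanged.

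The figures rest on a true ratio of 1 and a log-scale test. A true ratio above 1 would lower power and one below 1 would raise it; the other scales tried move the figures by a few points without changing the picture. The conflict between the fixed margin in Section 1.8 and the CV-dependent ratios in Section 1.7.1 rests on the text alone and needs none of these assumptions.

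**What to change.** 1. Replace the power sentence in Section 1.8 with: For the fixed 1.2 margin at one-sided 0.025 and a true ratio of 1, 42 per arm gives about 80% power at CV 0.3, 57% at CV 0.4 and 42% at CV 0.5.
2. State the reported CV used for each of SAPS, SANS and caregiver burden, and the scale of the analysis.
3. Reconcile Hypotheses 1.1 and 1.2 with Section 1.8, giving each outcome one prespecified margin that does not depend on the CV. The margin should not be raised to recover power.
4. State the alpha and power that go with the 1.17 burden bound: about 68%, 46% and 33% at CV 0.3, 0.4 and 0.5 if alpha is 0.025, and close to 80% at CV 0.3 only if one-sided alpha is 0.05.

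These are changes of text, with no new data and no change in enrolment. The cost is that the stated power becomes less favourable.

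### The ratio bound of 1.29 at CV 0.5 does not follow from the inputs in Section 1.8 (about 1.34 does), and Hypothesis 1.1 gives a third figure, 1.47, with no CV

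*Combined protocol and SAP*

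**What the plan says.** Section 1.8 sizes the trial on the ratio of the DSW mean to the in-person MFG mean, with higher scores worse. Its main power statement is: "With 42 subjects per treatment arm, power is >80% with one tailed alpha =0.025 to detect equivalence ratios of 1.2 (and above". It then describes the variability assumed: "CVs commonly range from 0.3-0.5 and within this range there were differences in the calculated equivalence ratios". It attaches two bounds to one alpha: "For alpha =0.025, and CV equal to 0.3 the equivalence ratio bound was 1.20 with an increase to 1.29 for a CV of 0.5". For caregiver burden the bound is "slightly smaller, it is 1.17 because there is only 1 primary measure".

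Section 1.7.1 restates the ratios inside the hypotheses. Hypothesis 1.1, for the Veteran outcomes (SAPS and SANS), is framed "with an equivalence ratio of 1.20-1.47 (depending on the coefficients of variance of the measures assessed". Hypothesis 1.2, for caregivers, is framed "with an equivalence ratio of 1.17-1.29 (depending the coefficient of variance of the measure assessed". Neither hypothesis names a CV or an alpha.

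**The concern.** The two bounds in the Section 1.8 sentence share one alpha and, as written, one sample size and one power. They should therefore differ only through the CV. The step from 1.20 to 1.29 looks too small for a CV that rises from 0.3 to 0.5. In addition, 1.29 is the upper end of the caregiver range in Hypothesis 1.2, while Hypothesis 1.1 takes SAPS and SANS up to 1.47.

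These ratios appear in the hypotheses for the primary outcomes. A reader of Section 1.8 would conclude that 42 per arm gives 80% power for a ratio of 1.29 when the CV is 0.5. A reader who also takes in Hypothesis 1.1 cannot tell which ratio the sample size supports.

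**Working it through.** **Inputs from Section 1.8:** 42 per arm, one-sided alpha 0.025, power 80%, CV 0.3 to 0.5. **Assumptions not in the documents:** a true ratio of 1, equal CVs in the two arms, and analysis on the log scale.

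**Formulas.** σ = √ln(1 + CV²). SE = σ·√(2/42). Power comes from the noncentral t with 82 df and noncentrality ln(R)/SE. The 80%-power bound is the R at which that power equals 0.80.

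**Reproducing the plan's 1.20.** At CV 0.3, σ = √ln(1.09) = 0.2936 and SE = 0.2936 × 0.2182 = 0.0641. The bound is 1.199, and power at 1.20 is 80.3%. The plan's figure is confirmed.

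**Same inputs at CV 0.5.** σ = √ln(1.25) = 0.4724 and SE = 0.1031. The bound is 1.339, not 1.29.

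| One-sided alpha, 42 per arm | CV 0.3 | CV 0.4 | CV 0.5 |
|---|---|---|---|
| 0.025 | 1.199 | 1.269 | 1.339 |
| 0.05 | 1.174 | 1.235 | 1.295 |

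**A check free of n, alpha and power.** With a true ratio of 1 and the same settings in both rows, ln(bound) is proportional to σ. From CV 0.3 to CV 0.5 it grows by 0.4724/0.2936 = 1.609. A bound that rounds to 1.20 (1.195 to 1.205) becomes 1.195^1.609 to 1.205^1.609, or 1.332 to 1.350. A bound that rounds to 1.17 (1.165 to 1.175) becomes 1.279 to 1.296. So 1.29 pairs with 1.17, not with 1.20.

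**Other formulas** (42 per arm, alpha 0.025; bounds at CV 0.3 and CV 0.5):

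- log scale, normal approximation: 1.197, 1.335
- log scale with σ = CV: 1.201, 1.358
- raw ratio, normal: 1.203, 1.366
- raw ratio, t: 1.206, 1.371
- difference scale: 1.186, 1.309

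**Other settings:**

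- A true ratio of 1.29/1.339 = 0.963 restores 1.29 at CV 0.5, but gives 0.963 × 1.199 = 1.155 at CV 0.3.
- Completers of 42 and 47, with the 10% variance inflation on MFG, give 1.198 and about 1.34.
- The enrolled numbers ("Given these estimates 70 in person MFG subjects will be enrolled and 47 DSW subjects"), with the same inflation and alpha 0.025, give 1.173 and 1.293.
- One-sided 0.05 with 42 per arm gives 1.174 and 1.295.

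The last two both reproduce the 1.17–1.29 of Hypothesis 1.2. Neither reproduces 1.20.

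**What 1.29 costs at CV 0.5.** With 42 per arm and alpha 0.025, power is 0.685. Reaching 80% takes 55 per arm, and at 55 per arm the CV 0.3 bound would be 1.17. With 42 per arm, 1.29 is the 80% bound at a CV of about 0.43.

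**The 1.47 in Hypothesis 1.1.** At alpha 0.025 with 42 per arm, 1.47 is the 80% bound at a CV of about 0.69.

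**The power statement at 1.2.** The largest CV with 80% power at 1.20 is 0.301. If non-inferiority is tested with a one-sided 97.5% confidence bound against a fixed 1.20 margin, power is 80%, 57% and 42% at CV 0.3, 0.4 and 0.5. These three figures do not describe the literal rule in Section 1.8, "Any ratio of DSW/MFG that is < 1.2 will cause us to reject the null hypothesis". Read as a comparison of the observed ratio with 1.2, that rule would declare equivalence with probability 0.998, 0.985 and 0.962 when the true ratio is 1.

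**The case against.** The strongest reply is that 1.47 may be correct. Section 1.8 describes 0.3 to 0.5 as the common range of CVs, not as a ceiling, and the normal formula at alpha 0.025 gives 1.471 at CV 0.7. On that reading 1.20–1.47 is a coherent range for CV 0.3 to 0.7, and the fault is only an unstated CV. This stands: 1.47 is not shown to be an arithmetic error. It still leaves the same outcomes with two upper ends and nothing to connect them.

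A second reply is that 1.34 is too firm, because the plan names its software but not the procedure, the scale or the true ratio. This stands in part. The formulas listed run from 1.31 to 1.37, and a two-sided equivalence version gives 1.40 at CV 0.5, though its CV 0.3 bound of 1.23 does not fit the plan. The exact replacement depends on the method. The mismatch does not, since no variant gives 1.20 and 1.29 together.

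Third, the fixed-margin power figures describe a confidence-bound test that Section 1.8 does not spell out, and the section does link 1.20 to CV 0.3 later in the same paragraph. Both are true, so those figures are offered only conditionally. But the sentence claiming more than 80% power carries no CV, and the decision rule uses a fixed 1.2.

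Finally, Hypothesis 1.2 contains no demonstrated error. Two different input sets reproduce it, so the idea that its upper end slipped into the alpha 0.025 sentence is plausible but unproven.

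**Conclusion.** The concern holds. The CV 0.5 bound in Section 1.8 is inconsistent with the CV 0.3 bound beside it. With 42 per arm and one-sided alpha 0.025 it should be about 1.34, and at the printed 1.29 power is about 68% where the text implies 80%. The 1.34 rests on a true ratio of 1, equal CVs and a log-scale analysis, a model supported by its reproducing the plan's 1.20. The 1.47 in Hypothesis 1.1 is a separate, unexplained inconsistency. The damage is limited to the stated design figures: 42 per arm at CV 0.3 stands and enrolment does not change. It should be fixed. Confidence is high that 1.20 and 1.29 do not belong together, and lower on how 1.29 arose.

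**What to change.** 1. Section 1.8: restate the CV 0.5 bound at alpha 0.025 as about 1.34, or as the value from a documented re-run, and name the method and the assumed true ratio.
2. Section 1.8: tie the claim of more than 80% power at 1.2 to CV 0.3. Add that, if non-inferiority is tested with a one-sided 97.5% confidence bound against a fixed 1.20 margin, power is about 80%, 57% and 42% at CV 0.3, 0.4 and 0.5.
3. Section 1.7.1, Hypothesis 1.1: reconcile with Section 1.8, either by giving 1.20–1.34 for CV 0.3 to 0.5 or by keeping 1.47 and stating the CV and alpha behind it.
4. Section 1.8 and Hypothesis 1.2: keep the single-measure reason for 1.17, and state the alpha and the numbers per arm behind 1.17–1.29. This item only supplies missing detail.

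The cost is restated figures and inputs in Section 1.8 and the two hypotheses, with no new data and no change to enrolment. The drawback is that the stated figures look less favourable.
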